# 5.7 Previous clinical experience with other ChAdOx1-vectored vaccines

ChAdOx1 is a replication incompetent adenovirus vector derived from wild type Chimpanzee adenovirus serotype Y25. ChAdOx2 is derived from another species E adenovirus, serotype C68 (AdC68, also known as SAdV25). Serotype Y25 and C68 share a close phylogenetic relationship, determined by analysis of nucleotide sequences of the hexon and fibre proteins. It may therefore be

REC Ref: <rec ref=""> IRAS project ID: 1007128 Protocol V2.0, 14th June 2023</rec>	CCHF01: A study of a new vaccine against Crimean-Congo Haemorrhagic Fever (a life- threatening tick-borne viral disease)	Page 24 of 78
---	--	---------------

anticipated that ChAdOx1- and ChAdOx2-vectored vaccines are likely to share similar safety and immunogenicity profiles.

To date, clinical trials have been conducted with 17 ChAdOx1 vaccines expressing different inserts that target either viral, bacterial, parasitic or cancer antigens (Appendix C). The most notable of these is ChAdOx1 nCoV-19, which has been authorised for use in many countries and has been used widely. Over 2 billion doses have been administered worldwide. Clinical trial and post-marketing experience with ChAdOx1 nCoV-19 has shown the vaccine to be well-tolerated, safe and effective against COVID-19. Serious side effects with ChAdOx1 nCoV-19 are extremely rare. The safety of ChAdOx1 nCoV-19 during pregnancy has been examined in clinical trial participants and a post marketing study. An analysis of pregnancies across ChAdOx1 nCoV-19 clinical trials included 72 pregnancies in ChAdOx1 nCoV-19 recipients and found no evidence of adverse pregnancy outcomes.

Other ChAdOx1-vectored vaccines that have been assessed in early phase clinical trials include vaccines for influenza (encoding the fusion protein NP+M1), tuberculosis (85A), prostate cancer (5T4), malaria (LS2), chikungunya (structural polyprotein), zika (prM and E), group B meningococcus (outer membrane protein), Middle East Respiratory Syndrome coronavirus (spike protein), ebola (Zaire and Sudan surface glycoproteins), and others. These trials have yielded positive safety and immunogenicity results. Many of these trials have been sponsored by the University of Oxford (Appendix D). A trial for a new vaccine against Nipah virus, ChAdOx1 NipahB, is currently being instigated.

## 5.8 Rationale for selected doses

The regimen and dose of ChAdOx2 CCHF (5 x  $10^{10}$  viral particles per dose, as a 2-dose administration) was selected on the basis of clinical experience with other ChAdOx1- and ChAdOx2-vectored vaccines, as well as other adenovirus vaccines (such as ChAd63).

ChAdOx1 nCoV-19 has been approved as a 2-dose schedule, administered 4 to 12 weeks apart, at a dose of 5 x  $10^{10}$  viral particles per dose (or equivalent). This regimen is well tolerated and immunogenic. Although approved as a 2-dose schedule, the vaccine is immunogenic following the first dose. The second dose significantly boosts binding and neutralising antibody responses to SARS-CoV-2. A 12-week interval between doses results in superior immunogenicity to a 4-week interval. The second dose produces lower rates of adverse reactions compared to the initial dose. Studies have demonstrated its efficacy following both a single and two-dose regimen.

Many clinical trials of ChAdOx1-vectored vaccines have included doses up to  $5 \times 10^{10}$  viral particles (see Appendix D). In every case, the safety and immunogenicity profiles were acceptable.

Two vaccines based on the ChAdOx2 platform have been assessed in phase 1 trials and found to be safe and well tolerated in doses up to  $5 \times 10^{10}$  vp (see Section 5.6).

Based on these data, this study will use a 2-dose regimen of ChAdOx2 CCHF, each containing 5 x 10^10 vp, given at a 12-week interval.

# 5.9 Potential risks to participants

Trial related risks are summarised below. Potential risks associated with ChAdOx2 CCHF are also discussed within the ChAdOx2 CCHF Investigator Brochure.

REC Ref: <rec ref=""> IRAS project ID: 1007128 Protocol V2.0, 14th June 2023</rec>	CCHF01: A study of a new vaccine against Crimean-Congo Haemorrhagic Fever (a life- threatening tick-borne viral disease)	Page 25 of 78
---	--	---------------

## 5.9.1 Risks related to ChAdOx2 CCHF

The most likely side effects that recipients of ChAdOx2 CCHF may experience are short-lived local (primarily injection site tenderness or pain) and systemic vaccine reactions (fatigue, headache, malaise, feverishness) that resolve completely within days.

There has been a far wider clinical experience with ChAdOx1- than with ChAdOx2-vectored vaccines, particularly with ChAdOx1 nCoV-19 (Oxford/AstraZeneca COVID-19 vaccine). As noted above in Section 5.7, because of the close similarity between these two platforms, it may be anticipated that ChAdOx1- and ChAdOx2-vectored vaccines are likely to share similar safety profiles.

The frequency of the commonest adverse reactions to ChAdOx1 nCoV-19 are shown in Table 6 below.

Adverse Reaction	Frequency (%)
Injection site tenderness	68%
Injection site pain	58%
Fatigue	53%
Headache	53%
Malaise	44%
Myalgia	44%
Feverishness	34%
Arthralgia	27%
Nausea	22%
Fever over ≥38°C	8%

Table 6: Frequency of commonest adverse reactions to ChAdOx1 nCoV-19

Rarer adverse reactions associated with ChAdOx1 nCoV-19 are shown in Table 8, Section 11.2.

Post-marketing experience with ChAdOx1 nCoV-19 has revealed a very rare but serious side effect following vaccination with ChAdOx1 nCoV-19 (which has also been associated with the adenovirus-vectored Johnson & Johnson COVID-19 vaccine). This is known as thrombosis with thrombocytopenia syndrome (TTS) or vaccine-induced immune thrombotic thrombocytopaenia (VITT). It can present with venous thrombosis, often at unusual sites, such as cerebral venous sinus thrombosis (CVST) and splanchnic vein thrombosis. The condition can also present with arterial thrombosis.. It can lead to death or serious long-term disability.

There has been marked geographical variation in the reporting rates of TTS/VITT. The WHO Strategic Advisory Group of Experts (SAGE) noted reporting rates have been far lower outside of the UK and EU, despite the widespread use of the vaccine in many countries outside of Europe. An analysis of the AstraZeneca global safety database has shown reporting rates (in the 21 days after vaccination) vary, with 17.6 cases per million doses in Nordic countries, 10.0 cases per million doses in the UK and 0.2 cases per million doses in Brazil, South Korea and the Philippines.

REC Ref: <rec ref=""> IRAS project ID: 1007128 Protocol V2.0, 14th June 2023</rec>	CCHF01: A study of a new vaccine against Crimean-Congo Haemorrhagic Fever (a life- threatening tick-borne viral disease)	Page 26 of 78
---	--	---------------

A review of 170 definite and 50 probable cases of VITT in the UK found a case mortality rate of 22%. Most cases occurred between 5 and 30 days after vaccination (median 14 days, maximum 48 days). The age range was 18 to 79 years (median, 48), with no sex preponderance and no identifiable medical risk factors. Another UK study of over 3.7 million recipients of ChAdOx1 nCoV-19 found that after the first dose there was an increased risk of venous thromboembolism (standardized incidence ratio: 1.12 [95% CI: 1.05 to 1.20]), and of cerebral venous sinus thrombosis (standardized incidence ratio: 4.14 [95% CI: 2.54 to 6.76]). Up to 23 November 2022, the MHRA had received Yellow Card reports of 445 cases of major thromboembolic events with concurrent thrombocytopenia in the UK following vaccination with ChAdOx1 nCoV-19 (221 in females, and 219 in males; age range from 18 to 93 years). Fifty-one of the 445 reports have been reported after a second dose. The overall case fatality rate was 18% with 81 deaths, six of which occurred after the second dose. Cerebral venous sinus thrombosis was reported in 161 cases (average age 46 years) and 284 had other major thromboembolic events (average age 54 years) with concurrent thrombocytopenia. The estimated number of first doses of COVID-19 Vaccine AstraZeneca administered in the UK by 23 November 2022 was 24.9 million and the estimated number of second doses was 24.1 million. The reported incidence of major thromboembolic events with concurrent thrombocytopenia following the first dose was higher in the younger adult age groups compared to the older groups (21.8 per million doses in those aged 18-49 years compared to 11.3 per million doses in those aged 50 years and over). This contrasts with incidence of these events after the second dose, which were commoner in the older age group (1.0 per million doses in those aged 18-49 years compared to 2.1 per million doses in those aged 50 years and over).

It is widely recognised that VITT is more likely to occur after a first dose of ChAdOx1 nCoV-19 than after a second dose. An international consortium has set up a registry which provides data on cases of cerebral venous sinus thrombosis occurring within 28 days of ChAdOx1 nCoV-19 vaccination. Of the 124 cases, 120 were after a first dose (61 definite, 20 probable, 10 possible, and 29 unlikely VITT), and 4 were after a second dose (1 definite, 1 probable, 1 possible, and 1 unlikely VITT). The interval between receiving the second vaccine dose and symptom onset varied between 1 and 6 days.

Cerebral venous sinus thrombosis (CVST) has been the most closely monitored manifestation of VITT. Using data from the European Medicines Agency's EudraVigilance database (until June 13, 2021), the absolute risk of cerebral venous sinus thrombosis (CVST) within 28 days of first-dose vaccination with ChAdOx1 nCoV-19was estimated to be 7.5 per million (95% CI: 6.9-8.3). In an age-stratified analysis, the absolute risk was the highest in the 18- to 24-year-old group (total CVST 11.0 per million [95% CI 5.0–23.9]). In the age groups 60 to 69 years and  $\geq$ 70 years, the risk of CVST was the lowest (2.2 per million (95% CI 1.4–3.3) and 1.3 per million (95% CI 0.6–2.9), respectively).

The pathophysiological mechanism behind VITT appears to be activation of platelets by antibody to platelet factor 4 (PF4). This closely resembles the pathophysiology of heparin-induced thrombocytopenia, which is also caused by anti-PF4 antibodies.

Other very rare serious reactions have been identified as part of post-marketing surveillance of ChAdOx1 nCoV-19 (Oxford/AstraZeneca COVID-19 vaccine). These include anaphylaxis, Guillain-Barré syndrome (GBS), transverse myelitis, capillary leak syndrome (CLS), and immune thrombocytopenic purpura (ITP). By 1st December 2022, the Yellow Card reporting system had received 888 reports of anaphylaxis or anaphylactoid reactions, 514 reports of suspected Guillain-Barré syndrome, 129

reports of transverse myelitis and 18 reports of capillary leak syndrome, after about 50 million doses of ChAdOx1 nCoV-19. The risk of ITP is about 5 cases per million doses of the vaccine.

It is currently unknown whether these very rare reactions will occur with other ChAdOx1- or ChAdOx2vectored vaccines. As ChAdOx2 CCHF has similarities to ChAdOx1 nCoV-19, participants will be informed about these conditions as part of the informed consent process for the trial. Investigators will be aware of potential signs of these conditions.

Given existing safety data which supports the use of ChAdOx1 nCoV-19 use in pregnant women, there is no reason to believe ChAdOx2 CCHF would be harmful to women or the foetus during pregnancy. However, there are no data on the use of ChAdOx2 CCHF in pregnancy. Therefore, pregnant women will be excluded from the trial and participants of childbearing potential will be required to use effective contraception (see section 8.3).

## 5.9.2 Other trial-related risks

Blood sampling during the trial may cause slight pain, bruising, light-headedness or fainting. The volume of blood taken in the trial is less than that taken by regular blood donors over the same period, so should not compromise healthy participants (for comparison, a *single* donation to the NHS blood bank would be approximately 470ml). Intramuscular injections carry a risk of bleeding in patients with very low platelet counts or coagulopathies. A baseline full blood count (with a platelet count) taken prior to vaccination reduces this risk.

The medical tests carried out during the trial screening and follow up have the potential to find incidental medical problems that may require referral of volunteers for further investigation. Participants will be informed of these, and, with their consent, their general practitioner (GP) will be contacted.

# 5.10 Potential benefits to participants

The recruitment population will not directly benefit from participation in the study. This is because the individual's risk of becoming infected with CCHF is currently low. Furthermore, ChAdOx2 CCHF clinical efficacy against CCHF infection has not been established and will not be established by this study. Participants will be informed that they should not anticipate any protection from potential future CCHF infection following participation in this study. No specific additional medical care will be provided through participation, and medical procedures are performed with the aim of determining eligibility and safety during the trial.

REC Ref: <rec ref=""></rec>	CCHF01: A study of a new vaccine against	Page 28 of 78
IRAS project ID: 1007128 Protocol V2.0, 14 th June 2023	Crimean-Congo Haemorrhagic Fever (a life-	
	threatening tick-borne viral disease)	

# 6 OBJECTIVES AND ENDPOINTS

# 6.1 Objectives, outcome measures and evaluation timepoints

Outcome	Objective	Outcome measure	Evaluation timepoints 
Primary	To assess the safety and tolerability of ChAdOx2 CCHF in healthy volunteers	
 
a) Occurrence of solicited local reactogenicity signs and symptoms
 
b) Occurrence of solicited systemic reactogenicity signs and symptoms
 
c) Occurrence of unsolicited adverse events (AEs)
 
d) Occurrence of abnormal safety laboratory measures
 
e) Occurrence of serious adverse events (SAEs) and adverse events
 
	7 days following each vaccination (D0 to D7; V2 to V2+7) 7 days following each vaccination
Secondary		of special interest (AESIs) Anti-CCHF glycoprotein specific serological response	Cohort 1 : D0, D28, V2, V2+28 Cohort 2 : D0, D28, V2, V2+28
	To compare the	Anti-CCHF glycoprotein specific serological response	Cohort 1 : D0, D28, V2, V2+28 Cohort 2 : D0, D28, V2, V2+28
Exploratory 	immunogenicity of ChAdOx2 CCHF vaccine in	a) Anti-CCHF glycoprotein specific serological response	Cohort 1 : D14, D56, V2+14, V2+56, V2+140, V2+280 Cohort 2 : D1, D14, V2+1, V2+14, V2+140, V2+280
		b) CCHF glycoprotein T cell response measured by IFN-γ ELISPOT	Cohort 1 : D0, D14, D28, D56, V2, V2+14, V2+28, V2+56, V2+140, V2+280 Cohort 2 : D0, D1, D14, D28, V2, V2+1, V2+14, V2+28, V2+140, V2+280
	-	a) Anti-CCHF glycoprotein specific serological response	Cohort 1 : D14, D56, V2+14, V2+56, V2+140, V2+280 Cohort 2 : D1, D14, V2+1, V2+14, V2+140, V2+280

individuals previously vaccinated with a ChAdOx vaccine with ChAdOx naïve individuals	b) CCHF glycoprotein T cell response measured by IFN-γ ELISPOT	Cohort 1 : D0, D14, D28, D56, V2, V2+14, V2+28, V2+56, V2+140, V2+280 Cohort 2 : D0, D1, D14, D28, V2, V2+1, V2+14, V2+28, V2+140, V2+280
Immunological profiling	
 
a) CCHF virus neutralising antibodies (using pseudoneutralization assays)
 
b) Cellular immune response to CCHF virus measured by ICS, proliferation and/or whole blood assays
 
c) Further immunological profiling
 
	Timepoints will be detailed in the laboratory analysis plan
To assess anti-vector immunity following vaccination	Binding and/or neutralising antibody responses against ChAdOx1	Timepoints will be detailed in the laboratory analysis plan
To investigate the relationship between the composition of the gut microbiota, vaccination and immunological outcomes	Characterisation of the gut microbiome composition and function	D0, D14, V2+14, V2+281

Visit and procedure timepoint windows are defined in section 0 (Schedule of Procedures). For any exploratory endpoints not completed prior to the end of the trial, where appropriate consent is received, samples will be transferred to OVC Biobank and analysed under the auspices of the OVC Biobank protocol and its ethical approval. (OVC Biobank HRA South Central - Hampshire B Research Ethics Committee, 21/SC/0161)

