One potential drawback to the use of adenoviral vector vaccines is that prior exposure to adenoviral antigens may lead to anti-vector immunity, dampening the potency of the vaccine. Our study will therefore compare immune responses to ChAdOx2 CCHF in participants who have previously received an adenoviral-vectored vaccine with the responses in adenoviral-vectored vaccine naïve participants.

REC Ref: <rec ref=""> IRAS project ID: 1007128 Protocol V2.0, 14th June 2023</rec>	CCHF01: A study of a new vaccine against Crimean-Congo Haemorrhagic Fever (a life-	Page 13 of 78
Protocol V2.0, 14 th June 2023	threatening tick-borne viral disease)	

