#### 5.3 ChAdOx2 CCHF vaccine

### 5.3.1 ChAdOx2 vector and ChAdOx2 CCHF

ChAdOx2 is a recombinant simian adenovirus viral vector developed by the University of Oxford. It was derived from wild-type replication-competent isolate AdC68 (species adenovirus E, also known as SAdV-25 and Pan 9), which has been rendered replication-deficient through deletion of the E1/E3 gene region (which is essential for viral replication), with further modification to the E4 region. To produce ChAdOx2 CCHF, a human codon optimised gene encoding CCHFV glycoprotein under the control of the short cytomegalovirus promoter was inserted into the vector. The viral vector was then rescued and grown in the HEK293 derived TRex cell line, prior to CsCl purification and sterile filtration.

The CCHFV M segment gene codes for a glycoprotein precursor (GPC). After expression, this is processed by a range of proteases into five glycoproteins: MCL, GP38, Gn, NSm, and Gc. Of these glycoproteins, the Gn and Gc subunits show greatest conservation across CCHFV strains. The Gn and Gc glycoproteins are the antigens found on the surface of CCHFV virus and are thought to be responsible for viral tropism and cell entry, though the cell surface target is unknown. Gn and Gc antigens have been shown to induce protective responses in some mouse challenge studies, and antibodies targeting Gc have been shown to neutralise CCHFV tec-VLPs (see Section 5.4).

The immunogenicity ChAdOx2 CCHF has been compared with a similar ChAdOx1-vectored vaccine (ChAdOx1- CCHFV GPC) in BALB/C mice. Vaccination with ChAdOx2 CCHF induced significantly greater anti-CCHFV Gc antibody titres in mice than vaccination with ChAdOx1- CCHFV GPC, although no further significant differences were measured between vectors with regards to cellular or neutralisation responses induced by vaccination.

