# 7 STUDY DESIGN

This is a multi-site, first-in-human, phase 1 trial to assess the safety, tolerability and immunogenicity of two doses of an intramuscular (IM) ChAdOx2 CCHF vaccine in healthy adults aged 18 to 55 years. There will be an initial lead-in cohort (Cohort 1) of 6 participants, followed by a cohort of 40 participants (Cohort 2), divided into two groups according to whether the participant has previously received a ChAdOx vaccine (Group A) or is ChAdOx vaccine naïve (Group B). All participants will receive two doses of ChAdOx2 CCHF, 12 weeks apart. All participants for cohort 1 will be recruited at the Oxford site; participants for cohort 2 may be recruited across any recruiting sites. The study is open-label and will not involve randomisation.

Volunteers will be recruited and vaccinated at the designated study sites.

REC Ref: <rec ref=""></rec> IRAS project ID: 1007128 Protocol V2.0, 14 th June 2023	(rimean ( ango Haemorrhagic Fever (a lite-	Page 30 of 78
---	--	---------------

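### The exploratory anti-vector outcome names ChAdOx1, so it does not directly measure antibody to the ChAdOx2 vector that participants receive

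*Protocol*

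**What the plan says.** The last rows of the table in protocol section 6.1 include the exploratory objective "To assess anti-vector immunity following vaccination". Its only outcome measure is "Binding and/or neutralising antibody responses against ChAdOx1". The third column of that row reads "Timepoints will be detailed in the laboratory analysis plan", so the timing is deferred but the target of the assay is not.

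On what is given, section 7 states: "All participants will receive two doses of ChAdOx2 CCHF, 12 weeks apart". On the vectors, section 5.7 says "ChAdOx1 is a replication incompetent adenovirus vector derived from wild type Chimpanzee adenovirus serotype Y25" and, of the study vector, "ChAdOx2 is derived from another species E adenovirus, serotype C68". Section 5.2 explains the interest in anti-vector immunity: "prior exposure to adenoviral antigens may lead to anti-vector immunity, dampening the potency of the vaccine".

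**The concern.** Immunity to the vector following vaccination would ordinarily be read as immunity to the vector in the vaccine just given. Here that vector is ChAdOx2, and no listed outcome names antibody to it. The protocol gives no reason for using ChAdOx1 in its place, and does not describe ChAdOx1 as a surrogate.

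At stake is how the anti-vector results can be interpreted. A ChAdOx-naive participant who makes antibody specific to ChAdOx2 after the first dose could read as negative. A previously vaccinated participant with ChAdOx1 antibody that does not recognise ChAdOx2 could read as positive. Both are possibilities that depend on cross-reactivity, not demonstrated errors. The outcome as worded could not show whether either had happened.

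**Working it through.** No arithmetic applies. The protocol has no power calculation (section 13.1.1), the 46 participants were chosen pragmatically (section 13.1.2), and no figure depends on this outcome. The check is to set the relevant sections side by side.

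1. **Vector given.** ChAdOx2, in both doses, to all participants (sections 5.3.1, 7 and 7.1).
2. **Vector measured.** ChAdOx1 only (section 6.1). The row reads complete, so this is not a gap left by the conversion of the table.
3. **Are they the same?** No. Section 5.7 derives ChAdOx1 from serotype Y25 and ChAdOx2 from serotype C68. It calls the two closely related on hexon and fibre nucleotide sequences, and expects similar safety and immunogenicity profiles. It says nothing about whether antibody to one binds or neutralises the other.
4. **Is the target left to a later document?** No. Only the timepoints go to the laboratory analysis plan.
5. **What an anti-ChAdOx1 titre means in each group**, using the definitions in sections 7.1 and 7.4:

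| Group | n | ChAdOx history | Before dose 1 | After a study dose |
|---|---|---|---|---|
| Cohort 1 | 6 | either | depends on history | response to ChAdOx2 seen only through cross-reactivity |
| Cohort 2, Group A | 20 | ChAdOx1 or ChAdOx2 vaccine at least 6 months earlier | direct measure of past ChAdOx1 exposure; indirect for any past ChAdOx2 exposure | earlier ChAdOx1 antibody plus whatever cross-reacts |
| Cohort 2, Group B | 20 | none | no earlier ChAdOx vaccine to detect | response to ChAdOx2 seen only through cross-reactivity |

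6. **Range.** The protocol does not give the degree of cross-reactivity, so it must be treated as unknown between two limits. With none, anti-ChAdOx1 titres in Group B carry no information on the response to the study doses. If it were complete, they would serve as a full surrogate. Nothing in the protocol places the trial between these limits.
7. **What depends on the outcome.** No primary or secondary outcome in section 6.1 uses it. The comparison of Groups A and B is made by vaccination history, on anti-CCHF serology and T-cell response, and stands whatever vector the assay targets.
8. **Are samples available?** Yes. The schedules in sections 4.2 and 4.3 draw about 50 mL of immunology blood at D0 and at V2 in both cohorts. Section 9.5.1 lists the blood draw before the injection, so the V2 sample is a pre-dose sample.

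**The case against.** The strongest reply is that ChAdOx1 is a sensible target here. Appendix C lists 18 ChAdOx1 products (one pending) against 2 ChAdOx2 products, and the only one marked licensed is ChAdOx1 nCoV-19. Section 5.6 describes the two ChAdOx2 trials, of 12 participants each; section 5.7 reports over 2 billion doses of ChAdOx1 nCoV-19. Group A will therefore very probably have been primed with ChAdOx1, and anti-ChAdOx1 antibody describes that exposure directly. This stands, and is a reason to keep ChAdOx1. It does not cover the objective as worded, which concerns immunity following vaccination, or Group B, which has no ChAdOx1 exposure to describe.

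A second reply is that the vectors are closely related, so the assay may well detect ChAdOx2 antibody. It may: the protocol does not rule this out. But sequence relatedness is not evidence of cross-binding or cross-neutralisation, and the protocol does not claim that it is.

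A third reply is that section 9.7.2.1 already permits other antibody assays and section 6.1 allows further immunological profiling, so a ChAdOx2 assay could be run without amendment. That is correct, but permission is not commitment, and the named outcome would still have the other vector as its target.

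A reader might go further and infer that the objective cannot be answered at all, or that the whole trial, with 46 participants and both doses, is compromised. The protocol supports neither. The first would require anti-ChAdOx1 assays to be uninformative about ChAdOx2, which is nowhere stated. The second treats one exploratory, descriptive row as if other results rested on it.

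**Conclusion.** The mismatch is certain from the protocol's own text; its practical effect is uncertain because cross-reactivity is not given. As written, the outcome does not directly measure antibody to the study vector, and the objective is at best partly answered: for immunity from earlier ChAdOx1 vaccination in Group A, and otherwise only so far as antibodies cross-react. The primary and secondary outcomes, the sample size and the comparison of CCHF responses between Groups A and B are unaffected.

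The point deserves correction but is not critical, because the outcome is exploratory. The protocol does not show whether ChAdOx1 was chosen deliberately or carried over by mistake. The conclusion assumes that the laboratory analysis plan, which is not at hand, does no more than section 6.1 assigns to it, namely set the timepoints.

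**What to change.** In section 6.1, change the target of the binding and/or neutralising antibody outcome from ChAdOx1 to ChAdOx2. Keep ChAdOx1 as an additional target if immunity from prior exposure is of interest. If ChAdOx1 alone was intended, the protocol should say so and justify it as a surrogate for the study vector. Carry the change into the laboratory analysis plan, using immunology blood already scheduled, including D0 and the pre-dose V2 sample.

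The cost is one line of text and at most one additional assay target. No visit, sample or blood volume is added. It is better done early: under section 9.7.5, remaining samples from participants who decline the Biobank are destroyed after the required storage period.

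Reporting the CCHF response by D0 anti-ChAdOx2 titre would be a useful option, but it is not part of this correction.
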